5.5 Subject Withdrawal and Discontinuation

All subjects enrolled in the study shall remain in the post market surveillance until they performed the 24 month follow-up or they experience an outcome (death, transplant, HM3 explant or exchange, or withdrawal), whichever comes first; however, a subject's participation in any clinical investigation is voluntary and the subject has the right to withdraw at any time without penalty or loss of benefit. Conceivable reasons for discontinuation may include, but not be limited to, the following:

- Physician or subject voluntary withdrawal
- Subject lost-to follow-up as described below
- Non-compliance with the PMS plan
- Subject is not on primary HM3 support

Sites must notify the Sponsor of the reason(s) for subject discontinuation. Investigators must also report this to their respective IRB as defined by their institution's procedure(s).

No additional follow-up is required, or data recorded from subjects once withdrawn from the post market surveillance, except for the status (deceased/alive).

Post Market Surveillance Plan

In case of subject withdrawal of consent, the site should make attempts to schedule the subject for a final post market surveillance visit. At this final follow-up visit, the subject will undergo the following assessments:

- Adverse events since the last follow-up
- Transplant, explant/exchange or device deficiency since the last follow-up
- Subject outcomes

Lost-to-Follow-up

If the subject misses two consecutive scheduled follow-up time points and the attempts at contacting the subject detailed below are unsuccessful, then the subject is considered lost-to-follow-up. Site personnel shall make all reasonable efforts to locate and communicate with the subject (and document these efforts in the source documents), including the following, at each contact time point:

- A minimum of two telephone calls on different days over the specified follow-up windows to contact the subject should be recorded in the source documentation, including date, time and initials of site personnel trying to make contact.
- If these attempts are unsuccessful, the site should send a letter (certified if applicable) to the subject.

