6.5 Subject Outcomes

Subjects will be followed until the 24-month follow-up is completed or until they experience an outcome, whichever occurs first. Outcomes include death, heart transplantation, HM3 exchange or explant, and withdrawal from the PMS. Outcomes must be reported to the Sponsor through the EDC system immediately upon discovery of the event.

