8.2.1 Primary Efficacy Endpoint

Primary efficacy endpoint is defined as the overall survival to transplant, myocardial recovery or on device support free of debilitating stroke (Modified Rankin Score >3) or reoperation for pump replacement during the 2-year surveillance period; this will be assessed using the Kaplan-Meier product-limit method along with a competing outcomes graph. Subjects who are urgently transplanted due to a HeartMate 3 malfunction will be considered to have experienced a primary endpoint event, as will subjects who expire, suffer a debilitating stroke or have their HeartMate 3 exchanged due to a device failure. Subjects who are transplanted (except as described above), explanted for recovery, withdraw from the trial or are lost to follow-up will be censored at that time in the analysis.

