#### 2.2.3 Primary Efficacy Endpoint

The primary efficacy endpoint will be assessed using the Kaplan-Meier Product-Limit method. Subjects without an outcome, as defined in section 1.4.1, will be censored at the time of an elective transplant, explant for recovery, withdraw from the trial, lost to follow-up or the end of the 24 months surveillance period; whichever occurs first. A competing outcome graph will also be presented.

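### Vital status is kept after withdrawal, but no analysis uses it: the primary Kaplan-Meier censors at withdrawal, which may bias the 24-month estimate if withdrawal is related to prognosis

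*Protocol*

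**What the plan says.** Protocol 5.5 ends data collection at withdrawal with one exception: "No additional follow-up is required, or data recorded from subjects once withdrawn from the post market surveillance, except for the status (deceased/alive". It gives no date of death, no last-known-alive date, no schedule for the check and no point at which checking stops. Among the possible reasons for discontinuation it lists "Physician or subject voluntary withdrawal" and "Non-compliance with the PMS plan".

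Death counts towards the primary efficacy endpoint. Protocol 8.2.1 treats subjects who are urgently transplanted for device malfunction as having an event, "as will subjects who expire, suffer a debilitating stroke or have their HeartMate 3 exchanged due to a device failure". SAP 1.4.1 agrees.

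Both documents censor at withdrawal. Protocol 8.2.1 says that subjects who "withdraw from the trial or are lost to follow-up will be censored at that time in the analysis". In SAP 2.2.3, subjects without an event "will be censored at the time of an elective transplant, explant for recovery, withdraw from the trial, lost to follow-up or the end of the" 24-month surveillance period.

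No other planned analysis takes up the retained status. Both documents plan a competing outcomes graph, but neither says that it uses information from after withdrawal. SAP 2.8 imputes nothing beyond the 6-minute walk rule. The SAP contents list names a sensitivity analysis section, but the body contains none: 2.11 (covariates) is followed by 2.12 (exploratory analysis).

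**The concern.** The plan keeps one item after withdrawal, and that item is a component of the primary endpoint. The analysis then sets it aside. Under the written rule, a death learned of only through the post-withdrawal status does not count.

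Censoring at withdrawal is unbiased only if withdrawn subjects have the same later risk as those who stay. In advanced heart failure, withdrawal by the physician or for non-compliance could track worsening health. The documents do not argue that it is unrelated to prognosis. The retained status is the one planned item that could test the assumption, but without dates it cannot enter a time-to-event analysis.

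At stake is the accuracy of the main descriptive estimate. No hypothesis test is at risk. SAP 2.4 also allows interim descriptive reports for regulatory or reimbursement purposes.

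**Working it through.** The documents state no event, withdrawal or power figure for this endpoint, so there is no figure of the plan's to reproduce. The checks below use assumed inputs, marked as such.

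**1. A cohort of 30.** The size is from Protocol 3.0. Assumed: events at Months 1, 3, 5, 9, 14 and 19, *w* withdrawals at Month 6, and everyone else event-free to Month 24.

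- Planned censoring: three events among 30 by Month 5 give 27/30 = 0.9. After Month 6, 27 − *w* are at risk and three more have events. The estimate is 0.9 × (24 − *w*)/(27 − *w*).
- Using dated vital status: if *d* of the withdrawn die before Month 24 and the rest are followed alive to Month 24, nobody is censored early. The estimate is the simple proportion (24 − *d*)/30.

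| *w* | Planned censoring | *d* = 0 | *d* = 1 | *d* = 2 | *d* = 3 |
|---|---|---|---|---|---|
| 1 | 0.9 × 23/26 = 79.6% | 80.0% | 76.7% | – | – |
| 2 | 0.9 × 22/25 = 79.2% | 80.0% | 76.7% | 73.3% | – |
| 3 | 0.9 × 21/24 = 78.8% | 80.0% | 76.7% | 73.3% | 70.0% |

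Each death is worth 1/30 = 3.3 points. With three withdrawals, the planned estimate (78.75% before rounding) is 1.25 points too low if none dies, and 2.1, 5.4 or 8.75 points too high if one, two or three die.

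**2. How likely is the worst case?** Take 79.0% two-year survival (MOMENTUM 3, Protocol 1.1.1) and a constant hazard. The chance of dying between Months 6 and 24 is 1 − 0.79^(18/24) = 16%, so three deaths out of three has probability 0.16³ ≈ 0.4%. At five times the hazard, the chance is 1 − 0.79^(5 × 18/24) = 59%, and 0.59³ ≈ 20%.

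**3. Large-sample bias.** Assumed: exponential event hazard λ and withdrawal hazard θ, with hazard *r*λ after withdrawal, *T* = 24 months, and all later events treated as deaths of known date. The censored Kaplan-Meier tends to e^(−λT). The event-free proportion that counts later deaths is

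e^(−(λ+θ)T) + θe^(−rλT)[1 − e^(−(λ+θ−rλ)T)]/(λ+θ−rλ).

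Example with 79% event-free, 10% withdrawal and *r* = 2: λT = −ln 0.79 = 0.2357 and θT = −ln 0.90 = 0.1054. The two terms are 0.7110 and 0.0702, which sum to 0.781. The bias is 0.790 − 0.781 = +0.9 points. A simulation of 2 million subjects per scenario gives, in points:

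| Withdrawal | *r* = 0.5 | *r* = 1 | *r* = 2 | *r* = 5 |
|---|---|---|---|---|
| 5% | −0.2 | 0.0 | +0.5 | +1.4 |
| 10% | −0.5 | 0.0 | +0.9 | +2.8 |
| 20% | −1.0 | 0.0 | +1.8 | +5.8 |

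With 74% (CE Mark trial) or 83.4% (ELEVATE) as the base, the range over all scenarios is −1.2 to +6.4 points. These bases are survival rates from Protocol 1.1.1, used as stand-ins for the composite.

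**4. Counting deaths alone is not enough.** In the example, let three withdraw and one die at Month 8. If the two survivors stay censored at Month 6, 25 are at risk after Month 6 and four have events: 0.9 × 21/25 = 75.6%. With the survivors kept at risk, the figure is 23/30 = 76.7%. Adding deaths but not survivors pulls the estimate down.

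**The case against.** The strongest reply is that the rule is deliberate and consistent. Protocol 6.5 says "Outcomes include death, heart transplantation, HM3 exchange or explant, and withdrawal from the PMS", so withdrawal ends follow-up by definition, and both documents censor there. When consent is withdrawn, Protocol 5.5 asks sites to attempt a final visit covering adverse events, device events and outcomes, so events before withdrawal are sought. The endpoints are not powered (note to SAP 1.4.3) and there is no success criterion (SAP 2.6). Sampling error is far larger than the shifts above: the exact 95% interval for 24/30 is 61% to 92%. All of this stands, and it limits the consequence. It does not explain why a component of the primary endpoint is retained and then never analysed.

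A reader might also draw four stronger conclusions that the documents do not support:

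- **The estimate is too favourable.** That holds only if withdrawn subjects do worse. No withdrawal rate or link to prognosis is given. The bias is zero at equal risk and slightly downward if they do better.
- **The sponsor already holds the correcting data.** Protocol 5.5 promises only a deceased/alive status, which could be a single check. It also cannot show a later debilitating stroke, pump exchange or urgent transplant.
- **The overstatement is 2.9, 5.9 or 8.8 points for one, two or three withdrawals.** Those figures require every withdrawn subject to die before Month 24.
- **Stopping for non-compliance ends vital-status collection.** The exception in Protocol 5.5 covers withdrawn subjects without distinguishing the reason.

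**Conclusion.** The point holds in a limited form. Vital status is kept after withdrawal, death is a primary event, the primary analysis censors at withdrawal, and nothing in either document uses the status or makes it usable by dating it. This follows from the text alone, whatever the withdrawal rate.

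The effect on the estimate is conditional. It is nil if withdrawal is unrelated to prognosis, upward by about 0.4 to 6.4 points if withdrawn subjects have two to five times the hazard, and downward by 0.2 to 1.2 points if they have half. These ranges assume 5% to 20% withdrawal and a 74% to 83.4% event-free base, and the upper end needs 20% withdrawal with five times the hazard. In a cohort of about 30, each omitted death is worth roughly 3 points. The consequence is a possibly biased descriptive figure, not a wrong decision. This is a cheap improvement.

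**What to change.** - **Protocol 5.5:** record the date of death or the last-known-alive date with the status, and check it through 24 months after implant where the subject's consent allows.
- **SAP 2.2.3:** keep the censored primary analysis. Add beside it a pre-specified sensitivity analysis, or a separate all-cause survival Kaplan-Meier (rates of survival are already a listed outcome in Protocol 4.0). Count documented deaths after withdrawal, up to 24 months, as events. Keep withdrawn subjects known to be alive at risk until their last-known-alive date.
- **With the result:** state that stroke, exchange and urgent transplant after withdrawal are not observed. A composite that carries living withdrawn subjects forward treats them as free of those events, so it should supplement the censored estimate and not replace it. The all-cause survival curve avoids this problem.

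The cost is one date field, a few SAP sentences and one extra Kaplan-Meier run, with a possibly less favourable figure as the downside. It is best done prospectively, because dates may be hard to recover later.

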5.6 Number of Subjects

All consecutive patients at the participating sites with a planned HM3 implant, that meet the HM3 commercially approved labelling indications, will be enrolled in the PMS. We expect, approximately 30 subjects will be enrolled.

5.7 Total Expected Duration of the Post market surveillance

Subject follow-up will occur at the time of Baseline/Enrollment, HM3 Implant, and at 1, 3, 6, 12 and 24 months post HM3 implant, unless the subject experiences an outcome. The total duration of the Post Market Surveillance is estimated to be 36 months.

Post Market Surveillance Plan

6.0 TREATMENT AND EVALUATION OF ENDPOINTS

6.1 Baseline/Enrollment

The assessments listed in **Table 1** should be performed prior to the HM3 implant.

Table 1: Pre-implant Baseline Assessments

Study Activity	Data Collection
Informed Consent	Explain post market surveillance study and obtain informed consent as described in section 5.2.2
Demographics	Age, height, gender, ethnic origin, blood type
General and Cardiac Medical History	
 • Etiology and duration of heart failure • Therapeutic intent (BTT/BTC/DT)¹ • Arrhythmias • Valve repair/replacement • History of organ transplant, stroke, TIA, smoking, bleeding², valve disease, hypertension, MI, peripheral non-CNS thrombosis/thromboembolism, substance abuse (drug/alcohol), drug/radiation toxicity, peripheral vascular disease, carotid artery disease, coronary artery disease, coronary stents, CABG, cancer, allergies, renal insufficiency/failure and psychiatric, head, ear, nose, throat, dermatological, coagulation, inflammatory, gastrointestinal, genitourinary, respiratory or endocrine disorders, cardiac arrest, aortic stenosis. • Cardiac rhythm management device • Intra-aortic balloon pump • Other pre-implant circulatory support • CardioMEMS™, MitraClip™
Vital Signs	Weight, blood pressure and method, and heart rate
Medications	Inotropes, Anticoagulation/Antiplatelet (aspirin, Persantine, Plavix, warfarin, Other), antibiotics, vasodilators, diuretics, anti-arrhythmic, ACEi, ARB and beta blockers.
Laboratory Assessments ³	Hemoglobin, hematocrit, white blood cell count, platelets, creatinine, estimated glomerular filtration rate, liver function tests (AST, ALT, total bilirubin, albumin, pre-albumin), blood urea nitrogen, INR, LDH.

This confidential document is the property of Abbott and shall not be reproduced, distributed, disclosed or used without the express written consent of Abbott

Post Market Surveillance Plan

Study Activity	Data Collection
Right Heart Catheterization ⁴	Central venous pressure (CVP) or right atrial pressure (RAP), systolic, diastolic and mean pulmonary artery pressure (PAS, PAD, PAM), pulmonary capillary wedge pressure (PCWP), cardiac output (CO), and cardiac index (CI)
Echocardiogram ⁴	Type of assessment, LVEF, LVEDD, LVESD, AI, MR, TR, PR, including severity and/or grade, and presence of LV or LA thrombus, and aortic valve opening ratio
Functional Capacity	6-minute Walk Test ⁵ , NYHA Class, INTERMACS Profile
Quality of Life	EQ-5D-5L quality of life questionnaire

¹ BTT – bridge to transplant; BTC – bridge to transplant candidacy; DT – destination therapy.

² Bleeding includes diverticular disease, diagnosed arteriovenous malformations (AVMs), GI ulcer(s), anemia and/or erythropoietin treatment.

³ Most recent results obtained within 30 days prior to implant will be permitted as baseline data.

⁴ If collected per standard of care, most recent results within 30 days prior to implant.

⁵ If subject is able, else reason must be provided if not performed.

6.2 Implant

The data in **Table 2** will be collected for each subject's HM3 implant procedure.

Table 2. Data to be collected at the time of HM3 implant.

Study Activity	Data Collection
HM3 System Information	VAD serial number, reference number and date of implant of entire implanted system
Implant Data	
 • Presence of intracardiac (LA or LV) thrombus • Concurrent procedures • Administration of factor VII, vitamin K or anti-fibrinolytic • Pump position • Apical cuff attachment method • Drive line related information • Transfusion of whole blood, packed red blood cells [PRBC], fresh frozen plasma [FFP], platelets, cryoprecipitate, or Cell Saver • Intraoperative medications • Cardiopulmonary bypass (CPB) time

This confidential document is the property of Abbott and shall not be reproduced, distributed, disclosed or used without the express written consent of Abbott

Post Market Surveillance Plan

	
 • ECMO • Total implant time • Location of outflow anastomoses • Additional post-implant MCS • Hematocrit value
Pump Parameters	Pump speed, flow, power and pulsatility index

6.3 Follow-Up Visit Assessments

The assessments listed in **Table 3** will be performed at all other visits (i.e. at 1, 3, 6, 12 and 24 months) post HM3 Implant, unless the subject experiences an outcome; for the purposes of this PMS a month is defined as 30 days. The required assessments, follow-up schedule, and associated visit windows (**Table 4**) are generally aligned with SOC LVAD patient follow up. All follow-up visits are based on the HM3 implant date.

Table 3. Follow-up visit assessments.

Study Activity	Definition
Subject Status	Whether the subject is on HM3 LVAD support, if not, what was the outcome the patient experienced (i.e. death, transplant, withdrawn, pump exchange or explant)
Vital Signs	Weight, blood pressure and method of blood pressure measurement, and heart rate
Pump Parameters	Pump speed, flow, power and pulsatility index
Medications	Inotropes, anticoagulation/antiplatelet (Aspirin, Persantine, Plavix, warfarin, Other), antibiotics, vasodilators, diuretics, anti-arrhythmic, ACEi, ARB and beta blockers.
Laboratory Assessments	Hemoglobin, hematocrit, white blood cell count, platelets, creatinine, estimated glomerular filtration rate, liver function tests (AST, ALT, total bilirubin, albumin, pre-albumin), blood urea nitrogen, INR, LDH.
Echocardiogram ¹	LVEF, LVEDD, LVESD, AI, MR, TR, PR, including new onset, severity and/or grade, and presence of LV or LA thrombus, and aortic valve opening ratio
Functional Capacity	6-minute Walk Test and NYHA Class
Quality of Life	EQ-5D-5L quality of life questionnaire

¹If collected per SOC.

The follow-up visit must occur within the designated window (**Table 4**). The assessments for a single visit do not have to occur on the same date, but must occur within the designated window, or will be considered a protocol deviation. The Sponsor understands that some lab results may be received several days after the visit has occurred, in these instances the date

This confidential document is the property of Abbott and shall not be reproduced, distributed, disclosed or used without the express written consent of Abbott

Post Market Surveillance Plan

the blood draw occurred will be considered as the date of the lab assessment. All subjects should be asked, at each follow up visit, if they were seen at an outside facility. If so, medical records from any facility that has seen the patient must, with the subject's consent, be requested and reviewed for potential adverse events.

Table 4. Follow-up visit windows.

Visit 0	Visit 1	Visit 2	Visit 3	Visit 4	Visit 5	Visit 6
Baseline/ Enrollment	Implant	Month 1 ± 7 days	Month 3 ± 30 days	Month 6 ± 30 days	Month 12 ± 30 days	Month 24 ± 60 days
Patients will be followed until the 24 months visit or they experience an outcome.						

6.4 Unscheduled Visits

6.4.1 Adverse Events

Relevant data related to adverse events will be collected as they occur. For additional details regarding adverse events, including mandated reporting timelines, refer to section 7.

6.4.2 Reoperations

Data related to any cardiac or non-cardiac reoperations, occurring after enrollment will be collected. Reoperations must be reported to the Sponsor through the EDC system within three days of awareness of the event or, at the latest, if the operation was unknown to the implanting site (i.e. occurring at another facility), during the next follow-up visit. For pump exchanges, additional implant data will be collected, including exchange status and pump exchange type.

6.4.3 Rehospitalizations

All rehospitalizations with associated reasons will be captured during the follow-up period for all subjects. While hospitalized, the follow-up visit assessments will continue to be performed according to the follow-up schedule. Hospitalizations must be reported to the Sponsor through the EDC system within three days of awareness or discovery of the event or, at the latest, if the hospitalization is unknown to the implanting site (i.e. occurring at another facility), during the next follow-up visit.

6.5 Subject Outcomes

Subjects will be followed until the 24-month follow-up is completed or until they experience an outcome, whichever occurs first. Outcomes include death, heart transplantation, HM3 exchange or explant, and withdrawal from the PMS. Outcomes must be reported to the Sponsor through the EDC system immediately upon discovery of the event.

6.6 Schedule of Events

All of the post market surveillance assessments and their schedule are listed in **Table 5**.

This confidential document is the property of Abbott and shall not be reproduced, distributed, disclosed or used without the express written consent of Abbott

Post Market Surveillance Plan

Table 5. Schedule of assessments.

Assessment	Baseline/ Enrollment	HM3 Implant	Month 1 ¹ (± 7 days)	Month 3 ¹ (± 30 days)	Month 6 ¹ (± 30 days)	Month 12 ¹ (± 30 days)	Month 24 (± 60 days)	As Occurs or Unscheduled
Eligibility Assessment	X							
Informed Consent	X							
Demographics	X							
General and Cardiac Medical History	X							
Right Heart Catheterization	X ²							X ²
HM3 Information		X						X ³
Implant Data		X						X ³
Vital Signs	X		X	X	X	X	X	X
Laboratory Assessments	X		X	X	X	X	X	X
Echocardiogram	X ²		X ²	X ²	X ²	X ²	X ²	X ²
Medications	X		X	X	X	X	X	X
Functional Capacity	X		X	X	X	X	X	X ²
EQ-5D-5L Quality of Life Questionnaire	X		X	X	X	X	X	X ²
Pump Parameters		X	X	X	X	X	X	X
Subject Status			X	X	X	X	X	X
Subject Outcome								X
Rehospitalizations								X
Adverse Events								X
Device Deficiencies ^{4,5}								X
Modified Rankin Score (MRS) Assessment ⁶								X
Reoperations (excluding primary implant)								X
Protocol Deviations	X	X	X	X	X	X	X	X
COVID-19 questions (if applicable)	X	X	X	X	X	X	X	X

Note: Patients will be followed until the 24 months visit or they experience an outcome, whichever comes first.

¹One month = 30 days.

²If performed as standard of care.

³Implant data for HM3 to HM3 exchange(s) and only relevant information for non-HM3 exchange.

⁴Device deficiencies that result in adverse events only. Please see section 7.3.2 for further information.

Post Market Surveillance Plan

Assessment	Baseline/ Enrollment	HM3 Implant	Month 1 ¹ (± 7 days)	Month 3 ¹ (± 30 days)	Month 6 ¹ (± 30 days)	Month 12 ¹ (± 30 days)	Month 24 (± 60 days)	As Occurs or Unscheduled
------------	-------------------------	-------------	------------------------------------	-------------------------------------	-------------------------------------	--------------------------------------	-------------------------	-----------------------------

⁵Device malfunction is included within the definition of Device Deficiency.

⁶ Required only if a stroke has occurred

